3.1.2. Phase 2 Trial Objectives

3.1.2.1. Primary Objective:

- To estimate the PFS of patients with advanced or metastatic RCC by RECIST 1.1 criteria in patients treated with axitinib and TRC105 compared to those treated with axitinib alone, following failure of one prior VEGF inhibitor.

3.1.2.2. Secondary Objectives:

- To estimate overall response rate by RECIST 1.1 and Choi criteria, including duration of response by RECIST 1.1
- To estimate the disease control rate (CR + PR + SD) at 16 weeks by RECIST 1.1 and Choi criteria
- To determine the frequency and severity of adverse events as assessed by NCI CTCAE (Version 4.0)
- To evaluate TRC105 immunogenicity as measured by Anti-Product Antibody (APA) concentrations
- To explore the effects of TRC105 on circulating angiogenic protein biomarkers

- To characterize the pharmacokinetic profile of TRC105 and axitinib

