4.1.3. End of Study Assessments

Assessments other than TRC105 pharmacokinetics (phase 1b and Arm B of phase 2), immunogenicity, and protein biomarkers only need to be completed if they were not completed during the previous 2 weeks on study (during the last 8 weeks on study for radiologic tumor assessments). The following will be performed according to the Schedule of Assessments (Table 7, Table 8, Table 9, Table 10, and Table 11).

- Physical examination including examination of all major body systems, ECOG performance status, and vital signs.
- Single tracing 12-Lead ECG (QT, PR and QRS intervals and heart rate will be captured).
- Thyroid function tests (i.e., thyroid stimulating hormone)
- Hematology and serum chemistry (including TSH) to be performed locally.
- Urinalysis to be performed locally. Microscopic analysis and/or urine protein-creatinine ratio (UPCR) should be performed as clinically indicated.
- Phase 1b **cohorts -1, 1, 2, and Expanded Cohort 1**: Blood sampling for TRC105 pharmacokinetics will include a pre-infusion trough sample and an end-of-infusion peak sample to be analyzed by a third party laboratory (see laboratory manual for specific instructions regarding collection times, procedures, processing, storage and shipment).
- Phase 1b **cohorts 3, 4 and Expanded Cohort 2**: Blood sampling for TRC105 and axitinib pharmacokinetics will include a trough sample to be analyzed by a third party

laboratory (see laboratory manual for specific instructions regarding collection times, procedures, processing, storage and shipment)

- Phase 2: Blood sampling for TRC105 and axitinib pharmacokinetics will include pre-dose trough samples to be analyzed by a third party laboratory (see laboratory manual for specific instructions regarding collection times, procedures, processing, storage and shipment).
- Phase 1b and Arm B of Phase 2: Blood sampling for immunogenicity to be analyzed by a third party laboratory (see laboratory manual for specific instructions regarding collection, processing, storage and shipment).
- Blood sampling for protein biomarker analysis by a third party laboratory (see laboratory manual for specific instructions regarding collection processing, storage and shipment)

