Axitinib ^[12]		28 Day Cycle					28 Day Cycle			28 Day Cycle		28 Day Cycle				
Tumor Assessments																
CT or MRI Scans ^[13]	X Including Brain	EVERY 56 DAYS FROM DATE OF RANDOMIZATION													X	
Bone Scans ^[13]	X															
Other Clinical Assessments																
12-Lead ECG ^[14]	X	X					X			X		X			X	
Concomitant Medications/Treatments ^[15]	X	X	X		X		X	X		X	X	X	X		X	
Baseline-Emergent Adverse Events ^[16]	X															
Adverse Events ^[16]		X	X		X		X	X		X	X	X	X		X	X
Special Laboratory Assessments																
Pre-Dose PK ^[17]		X					X					X			X	X
Anti-Product Antibody Testing(Arm B) ^[18]		X					X					X			X	X
Protein Biomarkers ^[19]		X					X					X			X	
Archival Tumor Tissue ^[20]	X															

Schedule of Assessments Footnotes Arm B (TRC105 + Axitinib) BIWEEKLY DOSING:

1. **Days of Treatment with TRC105:** All assessments should be performed prior to the TRC105 infusion and axitinib dosing unless otherwise indicated. Each cycle is 28 days in duration.
2. **Cycle 1 day 1:** Hematology (including Fe studies), blood chemistry (including TSH testing), coagulation, urinalysis, physical examination, ECG and pregnancy test not required if acceptable screening assessment is performed within 7 days prior to the start of treatment on cycle 1 day 1.
3. **End of Study:** Visit should generally occur within 7 days (+/- 1 day) of the last dose of TRC105 or axitinib. Assessments other than pharmacokinetics, immunogenicity and protein biomarkers do not need to be repeated if performed within the previous 2 weeks (previous 8 weeks for radiologic tumor assessments). Follow-up visits should occur 28 days following the last dose of TRC105 study drug as outlined in the Schedule of Assessments.
4. **Informed Consent:** Must be obtained prior to undergoing any study specific procedure and may occur prior to the 28-day screening period.
5. **Medical/Oncologic History and Demographics:** To include information on prior anticancer therapy.
6. **Physical Examination:** Examination of major body systems and ECOG performance status.

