 - Hemoglobin ≥ 9.0 g/dL without transfusion support within the past 14 days (erythropoietin or darbepoetin permitted)

-
- Serum creatinine \leq 1.5 times the upper limit of normal or creatinine clearance $>$ 30 mL/min by Cockcroft-Gault formula
 - INR between 0.8 – 1.2
9. Willingness and ability to consent for self to participate in study
 10. Willingness and ability to comply with scheduled visits, treatment plan, laboratory tests, and other study procedures
 11. Men who are sterile (including vasectomy confirmed by post vasectomy semen analysis) OR agree to use a condom with spermicide (refer to [Section 2.3.6.1](#)) and to not donate sperm during the study and for at least 180 days following last dose of TRC105 or axitinib.
 12. Woman of non-child bearing potential due to surgical sterilization (at least 6 weeks following surgical bilateral oophorectomy with or without hysterectomy or tubal ligation) confirmed by medical history or menopause (i.e., no menstrual bleeding for more than 12 months in a woman aged 45 years or more), OR woman of child bearing potential who test negative for pregnancy at time of enrollment based on serum pregnancy test and agree to use at least two acceptable methods of birth control, one of which must be highly effective (refer to [Section 2.3.6.1](#)) during the study and for at least 180 days after stopping TRC105 or axitinib (refer to [Section 2.3.6.1](#)).

5.1.2. Exclusion Criteria:

1. **PHASE 2 ONLY**: Prior treatment with TRC105 or axitinib or any agent targeting the endoglin pathway (including a fusion protein that binds bone morphogenic protein)
2. **PHASE 1B COHORT 3 AND 4 ONLY**: Prior treatment with TRC105
3. Grade 3 or 4 toxicity related to prior VEGF inhibitor that did not resolve to grade 1
4. Current treatment on another therapeutic clinical trial
5. Receipt of systemic anticancer therapy, including investigational agents, within 28 days of starting study treatment. If anticancer therapy was given within 28 days of starting study treatment, patients may be included if 5 times the elimination half-life of the drug passed.
6. Prior radiation therapy within 28 days of starting the study treatment, except radiation therapy for bone metastases or radiosurgery is permitted up to 14 days of starting treatment

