Safety will be assessed by examining vital signs, physical exams, clinical laboratory tests, and adverse events (AEs). These analyses will be conducted on the safety population. Descriptive statistics will be provided for safety variables.

Baseline will be defined as the last available measurement prior to First Dose. Where this definition does not apply, the definition for that analysis will be specified.

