12.7. ECOG Performance Status

The Eastern Cooperative Oncology Group (ECOG) performance grade scale will be used to measure patient ECOG performance status. The number and percent of patients in each grade category will be summarized at each visit for each dose level with individual patient data displayed in a listing.

13. Pharmacokinetic Analysis

Serum samples will be assayed to measure the concentration of TRC105 and axitinib. Only concentrations greater than or equal to the limit of qualification (LOQ) from the assay will be used. The following parameters will be determined:

- C_{\max} (ng/mL) [Maximal TRC105 concentration]
- C_{\min} (ng/mL) [Minimal TRC105 concentration]

Descriptive statistics of C_{\max} , C_{\min} , following drug administrations will be calculated by dose level and time of treatment (baseline versus patient withdrawal). Gender specific analysis will be performed if adequate data are available for each gender within a given dose cohort, e.g. the

expanded cohort at MTD. Summary PK analyses will include all patients and also include only those patients who develop positive titers for APA.

Listings of individual patient serum concentrations, actual blood sampling times, and pharmacokinetic parameters will be provided.

14. Additional Analysis

A listing of serum sample collections for anti-product antibody (APA) testing and the APA assay results will be provided. Also, the number and proportion of APA responses and changes in responses over time will be summarized. APA responses (Immunogenicity) will be measured utilizing a 3-tiered validated screening approach (screening, confirmatory, and titer) using a highly sensitive electrochemiluminescent bridging assay format.

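### SAP section 13 summarises PK only at baseline and withdrawal and gives axitinib no parameter, so the scheduled on-treatment troughs fall outside the specified summary

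*SAP*

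**What the plan says.** The Phase 2 secondary objectives include: "To characterize the pharmacokinetic profile of TRC105 and axitinib" (Protocol 3.1.2.2, repeated in SAP 2.2.2).

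SAP section 13 (Pharmacokinetic Analysis) begins: "Serum samples will be assayed to measure the concentration of TRC105 and axitinib". It then defines two parameters, both for TRC105: Cmax, and Cmin, glossed as "Minimal TRC105 concentration". Only values at or above the assay LOQ are used. The time rule is that descriptive statistics "following drug administrations will be calculated by dose level and time of treatment (baseline versus patient withdrawal".

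Section 13 does not say what baseline means for PK. The SAP's only general definition is in section 12 (Safety Analyses): "Baseline will be defined as the last available measurement prior to First Dose". That section adds that a different definition will be stated for any analysis where this one does not apply; section 13 states none.

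For End of Study in Arm B, footnote 3 of Protocol Tables 10 and 11 says: "Visit should generally occur within 7 days (+/- 1 day) of the last dose of TRC105 or axitinib". Table 9 sets the same window from the last axitinib dose in Arm A.

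**The concern.** The trial draws pre-dose samples throughout treatment, yet the one time rule in the SAP's PK section points to the two ends of treatment. Followed literally, the summary has one column with no drug in it and another that mixes near-troughs, part-intervals and washout. Neither describes exposure on treatment. Axitinib is assayed in both Phase 2 arms but is given no statistic.

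At stake is a secondary objective. A reader of the specified summary could not see what TRC105 trough each schedule maintained, or what axitinib exposure looked like in either arm. By contrast, SAP 12.3 and 12.5 summarise laboratory values and vital signs visit by visit.

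**Working it through.** The plan gives no figure to reproduce. The check sets the sampling schedule beside the two time points. CxDy means cycle x day y. The tables were machine-read, so the counts depend on their columns being aligned as they appear.

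**Baseline.**
- Protocol exclusion criterion 1 bars from Phase 2 anyone with "Prior treatment with TRC105 or axitinib or any agent targeting the endoglin pathway".
- Tables 9, 10 and 11 schedule pre-dose PK only, and the sole cycle 1 draw is C1D1. It therefore contains neither study drug, and the LOQ rule removes it.
- Table 7 (cohorts -1, 1, 2 and Expanded Cohort 1) shows no C1D1 PK draw, so those cohorts have no pre-first-dose sample.

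**Withdrawal.** Time from last dose to the End of Study visit is at most about 7 + 1 = 8 days. Against each dosing interval:
- Weekly TRC105, interval 7 days: a draw near day 7 is close to a trough.
- Every-two-week TRC105, interval 14 days: day 7 is 7/14, or half an interval.
- Axitinib, interval about 12 hours: 7 days is 7 × 2 = 14 intervals after the last dose.
- Arm B patients who stopped TRC105 but stayed on axitinib (allowed by Protocol 5.2, item 7): the footnote is met by the last dose of either drug, so it sets no limit on the time since the last infusion.

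**Peaks.** Phase 2 has no end-of-infusion sample, so the largest observed concentration there is not a peak. For the Table 7 cohorts, Protocol 4.1.3 says of End of Study: "Blood sampling for TRC105 pharmacokinetics will include a pre-infusion trough sample and an end-of-infusion peak sample to be analyzed by a third party laboratory". Table 7 schedules no infusion at that visit, so there is no peak to draw.

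**On-treatment draws in neither stratum.** Study day of CxDy = 28(x − 1) + y. For an illustrative duration I use the planning control PFS, 4.8 months × 30.4375 = 146.1 days.

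| Schedule | On-treatment pre-dose PK draws by day 146 | Count |
|---|---|---|
| Phase 2 (Tables 9–11) | C2D1 (29), C4D1 (85), C6D1 (141) | 3 |
| Phase 1b cohorts -1, 1, 2, Expanded Cohort 1 (Table 7) | C1D15 (15), C2D1 (29), C2D15 (43), C4D15 (99) | 4 |
| Phase 1b cohorts 3, 4, Expanded Cohort 2 (Table 8) | Days 1 and 15 of cycles 2–5 (29, 43, 57, 71, 85, 99, 113, 127), C6D1 (141) | 9 |

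With the duration implied for Arm B by the design hazard ratio under exponential PFS, 4.8/0.67 = 7.16 months, or about 218 days, C8D1 (day 197) is added and the Phase 2 count becomes 4.

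**Axitinib.** Pre-dose axitinib samples are scheduled in both Phase 2 arms and in the Table 8 cohorts. Section 13 defines no axitinib parameter, and the table lists in SAP 19.1 and 19.3 name only serum TRC105.

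**The case against.** The strongest reply is that other text covers these data. SAP 19.1 and 19.3 plan an in-text table of TRC105 PK parameters after repeated infusions. Section 13 lists every concentration with its actual sampling time, and the SAP listings include a final PK report. Protocol 9.1.1.1 plans population PK for TRC105, and Protocol 10.6 relates concentrations of both drugs to outcomes. A reader might infer from section 13 that the on-treatment troughs are never summarised. These provisions do not support that, least of all for TRC105. They do not close the gap either. The TRC105 table names no visits, so section 13 supplies its only time rule. Population PK omits axitinib, Protocol 10.6 is general, and listings are not summaries.

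Second, baseline is undefined for PK, and a Cmax following dosing cannot be a pre-first-dose value, so an early treatment period may be meant. That is fair: the term is ambiguous. In Phase 2, however, no cycle 1 draw follows a dose. Even if C2D1 were counted as baseline, every later trough would still be outside both strata.

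Third, a reader might infer that the withdrawal sample is never a trough. That goes too far. Weekly dosing is the default in Phase 2, and a draw about 7 days after the last infusion is close to a TRC105 trough.

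Fourth, no objective compares axitinib exposure between arms or tests attainment of the 200 ng/mL target, which comes from the background section. The randomised PFS comparison does not depend on either. This stands: both are optional additions. A between-arm ratio restricted to patients on one axitinib dose would condition on a post-randomisation variable, since Protocol 6.2.2 permits de-escalation in cycle 1.

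**Conclusion.** The point holds as a defect in the SAP's specification of a descriptive secondary analysis. The time rule in section 13 yields an essentially empty Phase 2 baseline cell and a withdrawal cell that is interpretable as a trough only for weekly TRC105 given about 7 days earlier. Three to four scheduled on-treatment troughs per Phase 2 patient fall in neither cell, as do four or nine per Phase 1b patient depending on the table. For TRC105 the gap is partly covered elsewhere. For axitinib there is no planned parameter or table at all.

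The counts use planning PFS as an illustrative treatment duration and the machine-read schedules. The empty baseline cell rests on reading baseline as before first dose, the only definition the SAP gives. The documents do not support saying that PK goes unanalysed or that the primary PFS result is affected. The change should be made, but the primary analysis does not depend on it.

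**What to change.** In SAP section 13:

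1. Replace the baseline-versus-withdrawal classification with nominal scheduled visit, by TRC105 schedule and actual dose, using each schedule's own draws:
   - Tables 9–11: C2D1 and day 1 of later even cycles.
   - Table 7: C1D15, C2D1, C2D15 and day 15 of later even cycles, with peaks only where an infusion is given.
   - Table 8: C2D1, C2D15, then days 1 and 15 of every later cycle, odd and even.
2. If the word baseline is kept for PK, define it.
3. Report End of Study and 28-day samples separately, by actual time since the last dose of each drug, and do not label them Cmin or Cmax.
4. Add a descriptive summary of axitinib troughs by arm and visit with the actual axitinib dose shown, and add the table to SAP 19.3. Label any between-arm ratio exploratory, because dose is determined after randomisation.

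The cost is SAP wording and a few extra tables. All the samples are already scheduled.

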4.1.1.2. Phase 2 Overview

This is a multicenter, randomized, phase 2 study of TRC105 in combination with standard dose axitinib in patients with advanced or metastatic renal cell carcinoma. Patients will be stratified by performance status (PS = 0 vs. PS = 1) and centrally randomized to one of the following treatment arms: TRC105 in combination with standard dose axitinib vs. standard dose axitinib, following documented progression on one prior VEGF inhibitor. All patients will initially receive axitinib 5 mg twice daily; patients randomized to receive TRC105 will receive TRC105 at 3 mg/kg on day 1, 7 mg/kg on day 4, and 10 mg/kg on day 8 and weekly thereafter.

TRC105 may be administered every two weeks starting with cycle 2 day 1 but **ONLY AFTER COHORT 3 AND 4 IN THE PHASE 1B ARE COMPLETE AND THE SPONSOR SENDS NOTIFICATION TO PROCEED WITH EVERY TWO WEEK DOSING.**

- Axitinib dosing will begin on cycle 1 day 1 and twice daily thereafter
- TRC105 at 10 mg/kg will be administered weekly during cycle 1.
 - The first weekly TRC105 dose will be split into two doses whereby 3 mg/kg is administered on cycle 1 day 1 and the balance is administered on cycle 1 day 4.
- Starting on cycle 2 day 1 and beyond, TRC105 may be administered every two weeks on days 1 and 15 at either 15 mg/kg or 20 mg/kg

Patients **in both arms** who tolerate axitinib for at least two consecutive weeks with no adverse reactions > Grade 1 considered clinically significant (according to the Common Toxicity Criteria for Adverse Events [CTCAE]), will, at the discretion of their treating physician, have the axitinib dose increased to 7 mg twice daily beginning on cycle 2 day 1, unless the patient's blood pressure is > 150/90 or the patient is receiving more than one antihypertensive medication. Subsequently, with the same criteria, patients who tolerate the axitinib dose of 7 mg twice daily for at least two consecutive weeks may have the axitinib dose increased to a maximum of 10 mg twice daily beginning with cycle 3 day 1. Dose reductions of axitinib and TRC105 are allowed per patient tolerance.

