Plasma levels of soluble angiogenic biomarkers will be listed by patient. Biomarker levels will be log-transformed before analysis, and analyses will be performed using baseline data from all available patients with continuous values for the protein analytes. PFS determined using univariate Cox proportional hazards models independent of treatment arm, and the resulting hazard ratios (HR), 95% confidence intervals (CI), and asymptotic P-values based on the score test will be reported. Multivariate Cox regression models will then test for interaction between marker level and treatment arm to identify markers predictive of benefit from axitinib or TRC105 and asymptotic P-values based on the Wald test for the interaction term will be reported. Biomarker levels will also be tested for interaction with each treatment arm separately. P-values will not be adjusted for multiple testing, and the results will be considered exploratory and hypothesis-generating. However, because high baseline levels of transforming growth factor-beta (TGF- β) receptor 3 and low baseline levels of osteopontin correlated with PFS and response rate in the Phase 1b study of TRC105 and axitinib, each of these biomarkers will be formally tested for correlation with PFS at the two-sided alpha level 0.05.

Hierarchical agglomerative clustering, using Euclidean distance and complete linkage, will be used to identify groupings among protein markers based on their baseline levels. The results will be illustrated using dendrograms. Forest plots will be created as illustrations of prognostic effect sizes (HRs and corresponding 95% CIs) with markers dichotomized as “high” or “low” relative to the median. Kaplan–Meier plots of PFS will also be created, with separate curves for each combination of treatment group by biomarker level. It has previously been shown in the Phase 1b study of axitinib and TRC105 that high baseline levels of TGF- β receptor 3 and low baseline levels of osteopontin correlated with PFS and response rate in the Phase 1b study of TRC105 and axitinib, so we will consider these biomarker levels dichotomized at the first quartile.

15. Changes from the Protocol-Specified Analysis

The details of analysis as indicated in this plan are based on the specifications of the 22Feb2016 version of the study protocol. Any later changes to the protocol may require consequential revision of this plan.

16. Programming Considerations

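### SAP Section 14 plans a marker interaction test inside each arm and a search for markers of axitinib benefit; this design can support neither, and the wording should be corrected

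*SAP*

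**What the plan says.** SAP Section 14 (Additional Analysis) plans four kinds of marker test against PFS.

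- **Pooled association:** "PFS determined using univariate Cox proportional hazards models independent of treatment arm", reported with a hazard ratio, 95% confidence interval and score-test p-value.
- **Between-arm interaction:** "Multivariate Cox regression models will then test for interaction between marker level and treatment arm to identify markers predictive of benefit from axitinib or TRC105", reported with a Wald p-value for the interaction term.
- **Per-arm test:** "Biomarker levels will also be tested for interaction with each treatment arm separately". No model or test statistic is given. Protocol Section 10.7 does not fill the gap, since it says only that biomarker data will be listed.
- **Formal test:** for TGF-beta receptor 3 and osteopontin, "each of these biomarkers will be formally tested for correlation with PFS at the two-sided alpha level 0.05". The reason given is that baseline levels of both correlated with PFS and response rate in Phase 1b.

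On treatment, Protocol Section 4.1.1.2 says of Phase 2: "All patients will initially receive axitinib 5 mg twice daily". The randomised comparison is TRC105 plus axitinib against axitinib alone.

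**The concern.** A predictive marker is one across whose levels the treatment effect changes. Showing that needs a treatment contrast. The per-arm sentence uses the word interaction for a test that has none, and the stated aim of the between-arm model includes a drug for which the trial has no contrast.

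The risk is one of interpretation. A marker that predicts outcome equally well in both arms may reach significance in one arm and miss it in the other through sampling error alone. Reported under the label of an interaction, it could be taken as a marker for selecting patients for TRC105, or for axitinib, when it says nothing about who benefits from either. The trial has a randomised control arm and already plans the test that answers the TRC105 question.

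**Working it through.** **What each model can test.** Let z = 0 for axitinib alone, z = 1 for TRC105 plus axitinib, and x = the log marker in standard deviation (SD) units. The two-arm Cox model is

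h(t | x, z) = h0(t) · exp(βx + αz + γxz).

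- The effect of adding TRC105 at marker level x is the log hazard ratio α + γx. It varies with the marker only if γ ≠ 0, so the predictive null is γ = 0.
- A model in Arm A alone estimates β and tests β = 0.
- A model in Arm B alone estimates β + γ and tests β + γ = 0.
- Neither one-arm test addresses γ = 0. If γ = 0 and β ≠ 0 (purely prognostic), both one-arm nulls are false and both tests should tend to reject.
- No term compares axitinib with its absence, because axitinib is given at both z = 0 and z = 1. Marker-dependent benefit from axitinib is therefore not identifiable. The term γ concerns only the addition of TRC105 to axitinib.

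**Information available.** The plan's event count is reproduced first. Inputs from SAP Section 4.2 are hazard ratio (HR) 0.67, one-sided alpha 0.10, 80% power and 1:1 allocation.

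- Schoenfeld: 4(1.2816 + 0.8416)² / (ln 0.67)² = 18.03 / 0.1604 = 112.4, so 113.
- Freedman: (1.2816 + 0.8416)² × (1.67/0.33)² = 4.508 × 25.61 = 115.4, so 116.
- The planned 115 lies between these. With 115 events the Schoenfeld power is 80.7%.

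That is about 115/2 = 57.5 events per arm for a one-arm marker model.

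**Approximate one-arm rejection rate.** At two-sided 0.05 with d events, the rate is approximately Φ(√d · ln HR − 1.96). The documents give no marker effect size, so a range is assumed.

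- HR 1.2 per SD: √57.5 × 0.182 = 1.38, giving 28%.
- HR 1.3 per SD: √57.5 × 0.262 = 1.99, giving 51%.
- HR 1.5 per SD: √57.5 × 0.405 = 3.07, giving 87%.

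**Simulation.** Each scenario used 3,000 trials with 75 patients per arm, exponential PFS, control median 4.8 months, treatment HR 0.67, 12-month uniform accrual, data cut at 115 events, and a standard normal marker with the same effect in both arms (γ = 0). Tests were two-sided at 0.05.

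| Marker HR per SD (assumed) | Arm A | Arm B | At least one arm | Exactly one arm | Marker-by-arm term |
|---|---|---|---|---|---|
| 1.0 | 5.6% | 5.9% | 11.1% | 10.8% | 5.6% |
| 1.3 | 52.8% | 46.7% | 75.3% | 51.1% | 4.9% |
| 1.5 | 86.1% | 80.8% | 97.2% | 27.5% | 5.5% |
| 2.0 | 99.9% | 99.8% | 100% | 0.3% | 5.3% |

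A hand check at HR 1.3, treating the arms as independent:

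- At least one arm: 1 − (1 − 0.528)(1 − 0.467) = 0.748.
- Exactly one arm: 0.528 × 0.533 + 0.467 × 0.472 = 0.502.

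Both agree with the table. Arm B rejects less often because it has fewer events when TRC105 works.

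**Fewer events.** SAP Section 4.2 allows the final analysis before 115 events. At 102 events and HR 1.3, the rates are 50% (Arm A), 41% (Arm B), 71% (at least one arm) and 5.6% (interaction), so the picture is unchanged.

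**The case against.** The strongest reply is that the SAP does not plan to call within-arm results predictive. It attaches that word once, to the between-arm model, which is the valid test and has its own p-value. The per-arm sentence carries no such claim. The forest plots are labelled as prognostic ("Forest plots will be created as illustrations of prognostic effect sizes"), and the general caveat reads "P-values will not be adjusted for multiple testing, and the results will be considered exploratory and hypothesis-generating". SAP Section 11.1 and Figures 14.2.2 to 14.2.5 also plan comparisons of the arms within levels of these two markers. All of this stands. A reader might infer that the SAP will report prognostic markers as predictive, but the documents do not say so. The risk comes from a misnamed test.

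A reader might also call the within-arm percentages false-positive rates. Against the null those tests actually address, no association in that arm, they are power. The HR 1.0 row shows each test close to its nominal 5%. They become errors only if a within-arm result is read as an interaction.

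The third tempting inference is that the formal tests of TGF-beta receptor 3 and osteopontin address the wrong hypothesis. The SAP describes them as tests of correlation with PFS and does not say which model carries them. Asking whether a Phase 1b association recurs is a legitimate aim. In simulation, a pooled test of a marker with HR 1.3 per SD rejects in about 76% of trials, which is power for that stated question. Moving the formal test to the interaction would change the question: such a marker would then be flagged only about 5% of the time.

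Two things survive the reply. The per-arm test is still named as something it cannot be. The reference to axitinib benefit sits inside the valid model's stated aim, so the validity of that model does not cure it. The word However, which introduces the formal tests, also sets those two markers apart from the exploratory caveat. Every Phase 1b patient received the combination, so that signal could not separate prognosis from prediction.

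**Conclusion.** The concern holds as a fault of specification and wording in SAP Section 14. Two statements there cannot be supported by the design: an interaction test within one arm, and identification of markers of benefit from axitinib.

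The size is conditional. If within-arm significance is taken as interaction, a purely prognostic marker with HR 1.3 per SD would appear to qualify in at least one arm in about 75% of trials, against about 5% for the marker-by-arm term. In about 51% of trials it would be significant in one arm only, which is the pattern most easily mistaken for selective benefit. These figures assume that effect size, a normally distributed log marker, proportional hazards and about 115 events. The interaction rate stays near 5% across the assumed range of 1.0 to 2.0.

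Consequences are limited. Primary PFS is untouched, most of the marker work is exploratory, and the correct test is already planned. The documents support neither a finding that the SAP intends to misreport markers nor a finding that the two formal tests are invalid.

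**What to change.** In SAP Section 14:

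1. Replace the per-arm sentence with: *Within-arm Cox models will estimate the association of the marker with PFS in each arm (HR, 95% CI); only the marker-by-arm interaction term in the model with both arms will be used to call a marker predictive.*
2. Restate the aim of the interaction model as finding markers *predictive of benefit from adding TRC105 to axitinib*.
3. Keep the two-sided 0.05 tests of TGF-beta receptor 3 and osteopontin as tests of association with PFS. State that they will be reported as prognostic and not used to claim prediction of TRC105 benefit. Placing the formal alpha on the interaction instead is open to the sponsor, but it is a choice of question and not a correction.

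The cost is SAP wording only. No new data, models or outputs are needed, and the primary analysis does not change.
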